8.3 Cost-effectiveness	16
9. ETHICAL CONSIDERATIONS	17
9.1 Regulation statement	17
9.2 Recruitment and consent	17
9.3 Benefits and risks assessment, group relatedness	17
9.4 Compensation for injury	17
9.5 Incentives	17
10. ADMINISTRATIVE ASPECTS AND PUBLICATION.....	18
10.1 Handling and storage of data and documents	18
10.2 Annual progress report	18
10.3 End of study report	18
10.4 Public disclosure and publication policy.....	18

SUMMARY

Rationale: In the Netherlands, diagnostics and treatment of fractures and dislocations are generally organized in the secondary care setting. In contrast, since January 2017 the general practice 'Zorgplein Lemmer' provides equal care for patients with non-complex fractures or dislocations. In this practice, regular X-ray diagnostics are used, which are digitally transmitted to the radiologist. When a non-complex fracture or dislocation is diagnosed, the for this purpose well-trained general practitioner provides the patient with a splint or sling and provides follow-up consults in his practice. While light trauma care is provided in several general practices in the Netherlands and healthcare professionals in both the general practice and the hospital are very satisfied with this provided care, it is unknown what the patient satisfaction level is and which determinants affect this patient satisfaction. Nowadays, substitution of care from the secondary to the primary care setting is stimulated by the government and insurers and in that light we aim to study the patient satisfaction of light trauma care for non-complex fractures or dislocations in the primary care setting in comparison to the secondary care setting. When the general practitioners in our study obtain similar results as the nearby hospitals, light trauma care may be substituted nationwide and beyond.

Objective: To assess patient satisfaction of light trauma care in the primary and secondary care setting. In addition, we aim to study demographic factors, treatment results, time consumption and costs to assess which determinants are responsible for the patient satisfaction.

Study design: Observational cohort study including patients presenting at the X-ray facility in the general practice 'Zorgplein Lemmer' and patients presenting at the X-ray facility of the Antonius Hospital Sneek, with non-complex fractures or dislocations.

Study population: 200 patients (≥ 12 years old) with fractures or dislocations which are non-complex such that they can be treated in the primary care setting. This sample size will allow us to demonstrate effect sizes of 0.4 (small to medium) or over with 80% (beta 20%) power using a two-sided alpha of 0.05.

Determinants: demographic factors (age, sex, comorbidity), nature of the trauma, treatment setting (in general practice or in the hospital, distance to treatment center), treatment results (functionality scores, complications, general health, quality of life), time consumption and costs.

Main study parameters/endpoints:

Primary:

- Patient satisfaction (questionnaires after 1, 6, and 12 weeks)

Secondary:

- General health (GHQ questionnaire), age, SES (after 1 week)
- Complications (e.g. secondary dislocation and pain scores; questionnaire after 12 weeks)
- Physical function (questionnaire after 12 weeks)
- Time consumption (questionnaires after 1, 6, and 12 weeks)
- Costs (economic evaluation; questionnaire after 12 weeks).

Nature and extent of the burden and risks associated with participation, benefit and group relatedness:

Since this is an observational study using a limited number of questionnaires in patients who receive regular care, there is no risk associated with participating in this study. The burden for participating patients will very low because they will only be asked to fill in a few questionnaires, which take about one and a half hours in total to fill in.

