6.1.2 Secondary study parameters/endpoints

1. Patient satisfaction measured using the PSQ-18 (1 and 6 weeks after treatment).

Marshall GN Hays RD. The Patient Satisfaction Questionnaire Short-Form (PSQ-18). Santa Monica, CA: RAND, 1994.

2. Complications of treatment and pain scores (12 weeks after treatment).
3. Physical functioning according to the 12-item World Health Organisation (WHO) Disability Assessment Schedule II (12 weeks after treatment).

*World Health Organization Disability Assessment Schedule II (WHO-DAS II)
WHO, Geneva (2000) www.who.int/icidh/whodas/whodasversions/12int.pdf*

4. Limitations in functions of upper extremities (if applicable) according to the Disabilities of the Arm, Shoulder and Hand (DASH) questionnaire (12 weeks after treatment).

5. General health status according to the 12-item General Health Questionnaire (GHQ-12; 12 weeks after treatment).

Goldberg, D. P. (1972). The Detection of Psychiatric Illness by Questionnaire. Maudsley Monograph No. 21. Oxford University Press: Oxford.

6. Quality of life using the EQ5D questionnaire (12 weeks after treatment).

Euroqol Group (1990) Euroqol—a new facility for the measurement of health-related quality of life. Health Policy 16:199–208

7. Time consumption (waiting time, treatment time, travelling time and distance; 1, 6, and 12 weeks after treatment).

8. Costs (12 weeks after treatment).

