6.1.3 Other study parameters

Baseline data: age, gender, social economic status, location and severity of the trauma (1 week after treatment).

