8.2 Secondary analyses

Secondary analyses will be conducted using data from all enrolled patients. Initially, univariable statistical tests (eg, χ^2 test or Fisher's exact test for categorical variables; t test or Wilcoxon rank-sum test for continuous variables) will be used to evaluate differences in outcome scores between the two treatment groups. Subsequently, data will be analyzed using multivariable regression models to estimate differences in mean patient satisfaction scores using possible predictors (eg, complications, pain scores, physical functioning, EQ-5D, time consumption) between both treatment groups.

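### Function and quality of life at 12 weeks are compared between non-randomised settings with no pre-injury score and no adjusted model, so prior disability can appear as, or hide, a treatment result

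*Combined protocol and SAP*

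**What the plan says.** The Summary, under Determinants, groups several patient-reported scores as "treatment results (functionality scores, complications, general health, quality of life"). Their timing is set in section 6.1.2:

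- "Physical functioning according to the 12-item World Health Organisation (WHO) Disability Assessment Schedule II (12 weeks after treatment")
- "Disabilities of the Arm, Shoulder and Hand (DASH) questionnaire (12 weeks after treatment"), where applicable
- "General health status according to the 12-item General Health Questionnaire (GHQ-12; 12 weeks after treatment")
- "Quality of life using the EQ5D questionnaire (12 weeks after treatment")

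For the GHQ the Summary gives another time point: "General health (GHQ questionnaire), age, SES (after 1 week").

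Section 6.1.3 defines the baseline set as "Baseline data: age, gender, social economic status, location and severity of the trauma (1 week after treatment"). It contains no function, health or quality-of-life score. Comorbidity is a determinant in the Summary but is missing from this list.

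Section 6.2 states that there is no randomisation, and section 6.3 assigns the analysis group by place of recruitment. Sections 4.2 and 4.3 admit patients from age 12 with no upper age limit and no exclusion for existing disability.

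Section 8.2 uses univariable tests "to evaluate differences in outcome scores between the two treatment groups". Its multivariable models have satisfaction as the outcome, with physical functioning and EQ-5D among the candidate predictors. Section 8.3 plans a between-group QALY difference, and EQ-5D is the only utility measure described.

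**The concern.** A disability or quality-of-life score at 12 weeks combines the patient's state before the injury with recovery from it. In a cohort running from adolescents to the very old, the first part can be large. Randomisation would balance it in expectation, but this study has none.

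Three uses of the scores are exposed:

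- **Setting comparison (section 8.2).** If one setting's patients were more disabled before the injury, an unadjusted test attributes the difference to care, or hides a real difference in the other direction.
- **QALY difference (section 8.3).** It rests on the same 12-week EQ-5D and takes over the same imbalance.
- **Satisfaction models (section 8.2).** Long-standing poor function can appear as a treatment result that drives satisfaction.

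Unlike an analysis choice, a missing questionnaire item cannot be repaired once the data are in.

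**Working it through.** **1. The plan's own figure.** For a standardised difference of 0.4, 80% power, two-sided 5% and equal groups (section 4.4), the normal approximation gives 99 per group, 198 in total. The t-test gives 99.08, so 100 per group and 200 in total, as stated. Power at 100 per group is 80.4% (t-test). This figure rests on satisfaction, and nothing below changes it.

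**2. What is available for adjustment.**

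| Score | Time point | Pre-injury value | Adjusted between-setting model |
|---|---|---|---|
| WHO-DAS II | 12 weeks | none | none stated |
| DASH | 12 weeks | none | none stated |
| EQ-5D | 12 weeks | none | none stated |
| GHQ-12 | 12 weeks (6.1.2) or 1 week (Summary) | none; both follow the injury | none stated |

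**3. Spurious difference and false-positive rate.** From the documents: 100 per group, two-sided 5%. Assumed: within-group SD of 1, correlation r of 0.5 to 0.7 between pre-injury and 12-week score, a pre-injury difference between settings of d SD, and no true setting effect.

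Spurious difference = r × d. Standard error = √(2/100) = 0.141. Rejection rates are from the noncentral t distribution with 198 degrees of freedom.

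| d (SD) | r × d (SD) | False-positive rate |
|---|---|---|
| 0 | 0 | 5% |
| 0.1 | 0.05–0.07 | 6–8% |
| 0.2 | 0.10–0.14 | 11–17% |
| 0.3 | 0.15–0.21 | 18–32% |

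**4. Adjustment with a perfectly measured pre-injury score.** The bias is 0 and the false-positive rate 5%. The interval width is multiplied by √(1 − r²), which is 0.866 at r = 0.5 and 0.714 at r = 0.7, a narrowing of 13–29%. This is the best case.

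**5. Adjustment with imperfect recall.** Assumed: reliability λ = 0.7, d = 0.3, and recall error that is random and equal in both settings.

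- Remaining bias = r × d × (1 − λ): 0.5 × 0.3 × 0.3 = 0.045 SD and 0.7 × 0.3 × 0.3 = 0.063 SD.
- Width factor = √(1 − r²λ): √0.825 = 0.908 and √0.657 = 0.811, a narrowing of 9–19%.
- False-positive rate: about 6% at r = 0.5 and 8% at r = 0.7, against 18% and 32% unadjusted.
- At λ = 0.5 the rate is 9–14% and the narrowing 7–13%.

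**The case against.** The strongest reply is about scope. The primary endpoint is PSQ-18 satisfaction at 12 weeks, the sample size rests on it, and satisfaction with this episode of care has no pre-injury value. A reader might infer that the main comparison is biased by the missing score. The documents do not support that, and the objection stands in full.

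Second, the secondary objective asks which determinants explain satisfaction. Health status at 12 weeks is a legitimate predictor whatever its origin, so for that use the fault lies mainly in the label. This also stands: the pre-injury score is needed there only if the coefficient is to be read as an effect of treatment.

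Third, a reader might infer that the case for substitution depends on similar function or quality of life. In the rationale, the sentence on similar results directly follows the aim of studying satisfaction, so that wider reading is an interpretation.

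Fourth, comorbidity might cover prior ill-health. It is at best a partial proxy, it is absent from the section 6.1.3 list, and no adjusted model for these outcomes is stated in which it could be used. A GHQ at 1 week, if the Summary is right, would still follow the injury.

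Fifth, imbalance may be small. Both groups come from one region, meet the same injury criterion and are to be recruited consecutively, with eligibility assessed by general practitioners near Lemmer. These features may limit imbalance but do not guarantee balance. For this reason the illustration starts at zero.

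**Conclusion.** The gap is real and affects secondary analyses: the between-setting comparison of function and quality of life, the QALY difference, and any reading of 12-week scores in the satisfaction models as treatment results. As the plan stands, these scores have neither a pre-injury value nor an adjusted model.

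The size cannot be read from the documents. For r of 0.5 to 0.7 the false-positive rate runs from 5% with no imbalance to 18–32% at 0.3 SD. A reader might take the upper figures as the expected error rate. They hold only under that assumed imbalance, which nothing in the documents supports or excludes. Nor should a full return to 5% be promised, because that requires error-free recall. About 6–8% is the figure at an assumed reliability of 0.7, a 0.3 SD imbalance and recall error that does not differ by setting.

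The change is worth making because it is cheap and can only be made before the data are collected.

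**What to change.** - **Week-1 questionnaire.** Add the 12-item WHO-DAS II and the EQ-5D, worded for the period just before the injury. Record comorbidity there and add it to section 6.1.3.
- **Section 8.2, outcome scores.** Analyse the 12-week WHO-DAS II and EQ-5D by linear regression on setting, with the patient's own pre-injury score, age, sex and comorbidity as covariates.
- **Section 8.3.** Adjust the QALY difference for the pre-injury EQ-5D.
- **Section 8.2, satisfaction models.** Enter the pre-injury score next to the 12-week score wherever the coefficient is to be read as a treatment result. Otherwise call the predictor health status at 12 weeks.
- **DASH and GHQ-12.** Describe them as health status at the time of measurement, and reconcile the GHQ time point between the Summary and section 6.1.2.

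The sample size of 200 is unchanged. The cost is one questionnaire amendment, a specified regression model, and a few more minutes for patients on top of about 1.5 hours. Recall error, including error that might differ by setting because recall follows treatment, remains and should be stated as a limitation.

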1. INTRODUCTION AND RATIONALE

In the Netherlands, diagnostics and treatment of bone fractures and dislocations are generally organized in the secondary care setting. When a fracture or dislocation is presumed, most general practitioners refer the patient to an X-ray facility in a nearby hospital. When the fracture or dislocation is confirmed, an emergency care doctor or trauma surgeon generally provides the treatment and follow-up. In contrast, since January 2017 the general practice 'Zorgplein Lemmer' provides equal care for patients with non-complex fractures or dislocations. In this practice, regular X-ray diagnostics are used, which are digitally transmitted to the radiologist. When a non-complex fracture or dislocation (a so-called 'light trauma') is diagnosed, the for this purpose well-trained general practitioners provide the patient with the usual care (e.g. a splint or sling) and provides follow-up consults in his practice. While light trauma care is provided in several general practices in the Netherlands and healthcare professionals in both the general practice and the hospital are very satisfied with this provided care, it is unknown what the patient satisfaction level is and which determinants affect this patient satisfaction. Nowadays, substitution of care from the secondary to the primary care setting is stimulated by the government and insurers and in that light we aim to study the patient satisfaction of light trauma care for non-complex fractures or dislocations in the primary care setting in comparison to the secondary care setting. When the general practitioners in our study obtain similar results as the nearby hospitals, light trauma care may be substituted nationwide and beyond.

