2. OBJECTIVES

Primary Objective:

To assess patient satisfaction of light trauma care in the primary and secondary care setting.

Secondary Objective(s):

In addition, we aim to study demographic factors, treatment results, time consumption and costs to assess which determinants are responsible for the patient satisfaction.

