4.4 Sample size calculation

The sample size calculation has been performed based on the difference in patient satisfaction. There was no literature available concerning patient satisfaction in trauma care in general practices or hospitals. Therefore, we based our sample size calculation on an estimated effect size. With a significance level of 5%, a power of 80% and equal treatment groups, a sample size of 200 patients (100 per group) was calculated. This sample size will allow us to demonstrate effect sizes of 0.4 (small to medium) or over.

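### The rationale rests on similar results in practice and hospital, but the plan does not make the practice-minus-hospital difference with its confidence interval the primary result, and its difference tests cannot show similarity

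*Combined protocol and SAP*

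**What the plan says.** - **Use of the comparison.** The Summary (Rationale) and section 1 both link similarity to policy: "When the general practitioners in our study obtain similar results as the nearby hospitals, light trauma care may be substituted nationwide and beyond". Neither defines similar.
- **Objectives.** Section 2 has a descriptive primary objective, "To assess patient satisfaction of light trauma care in the primary and secondary care setting", and a secondary one, "to assess which determinants are responsible for the patient satisfaction".
- **Sample size.** The Summary says that 200 patients can show "effect sizes of 0.4 (small to medium) or over with 80% (beta 20%) power using a two-sided alpha of 0.05". Section 4.4 explains where the 0.4 comes from: "Therefore, we based our sample size calculation on an estimated effect size". It is a detectable difference and is not called a margin.
- **Primary analysis.** Section 8.1 reports 12-week satisfaction with a 95% interval for each treatment group. It adds univariable and multivariable regressions of satisfaction, without naming the contrast of interest or any covariate.
- **Secondary analyses.** Section 8.2 plans tests of difference between the groups, then multivariable regression to estimate the difference in mean satisfaction between them. The example predictors are complications, pain, physical functioning, EQ-5D and time consumption. No interval is attached.
- **Available variables.** Treatment setting is among the determinants in the Summary: "demographic factors (age, sex, comorbidity), nature of the trauma, treatment setting (in general practice or in the hospital". Section 6.1.3 lists "Baseline data: age, gender, social economic status, location and severity of the trauma (1 week after treatment").

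**The concern.** Similarity is the finding that the rationale would use to support wider substitution of care. A report could follow the plan exactly and give two group intervals and a non-significant test. A reader could take that as evidence of similarity while the data still allow a moderate deficit in the practice. Two group intervals that overlap do not show which differences are excluded; only the interval for the difference does.

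The regression in 8.2 does not clearly fill the gap. Its example predictors are outcomes of care (complications, pain, function, quality of life) or features of how care is delivered (waiting, treatment and travel time). If setting affects satisfaction partly through these, adjusting for them removes part of the effect being compared, or otherwise distorts it. They suit the determinants objective in section 2, but not an estimate of how the two settings differ.

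**Working it through.** All figures are in SD units, because the documents give no SD for the PSQ-18.

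**Inputs from the documents.** Effect size 0.4, two-sided alpha 0.05, power 80%, 100 per group (Summary and section 4.4). **Assumed:** true deficits of 0.2, 0.3 and 0.4 SD; complete 12-week data in the main case; 20% loss as a variant.

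**1. The plan's own figure.** n per group = 2 × (1.960 + 0.842)² / 0.4² = 98.1, so 99. The t-test version gives 99.1, so 100. The stated 200 is reproduced. It is the size for a two-sided difference test with no allowance for loss.

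**2. Precision of the difference.** SE = √(2/100) = 0.1414. The 95% half-width is 1.96 × 0.1414 = 0.277, about 0.28 SD. A result that only just misses significance therefore has an interval reaching about 2 × 0.28 = 0.56 SD, beyond the 0.4 SD the study is sized to detect.

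**3. Chance of a non-significant test when the practice is truly worse** (two-sample t-test, two-sided 5%):
- 100 per group: 71% at 0.2 SD, 44% at 0.3 SD, 20% at 0.4 SD.
- 80 per group (assumed 20% loss): 76%, 53% and 29%, with a half-width of 1.96 × √(2/80) = 0.31 SD.

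**4. How often a non-significant result still allows a 0.4 SD deficit** (100 per group, normal approximation). The lower limit falls below −0.4 when the estimate is below −0.4 + 0.277 = −0.123. A negative estimate is non-significant when it is above −0.277. So the estimate must lie between −0.277 and −0.123.
- True deficit 0.3 SD: Φ((0.3 − 0.123)/0.1414) − Φ((0.3 − 0.277)/0.1414) = Φ(1.25) − Φ(0.16) ≈ 0.895 − 0.564 = 0.33. About 33% of all studies are thus non-significant with an interval that includes a 0.4 SD deficit. This is 76% of the 44% that are non-significant (0.76 × 0.44 = 0.33).
- No true difference: Φ(−0.87) − Φ(−1.96) ≈ 0.193 − 0.025 = 0.168. Divided by 0.95, this is 18% of non-significant results.

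A non-significant test thus leaves open whether the deficit is negligible or moderate. The interval for the difference shows it directly.

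**The case against.** The strongest reply is that no similarity claim is planned. The sentence is background and is hedged. The objective is only to assess satisfaction and its determinants, and a descriptive cohort needs no margin. Section 8.2 already plans to estimate the difference between settings, and any regression output would supply an interval. The figures in step 4 also depend on an assumed true deficit and on the test being non-significant.

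Most of this stands, and it limits the point. Four stronger readings that a reader might infer are not supported:
- *That the study is an equivalence or non-inferiority study lacking its margin.* No such hypothesis is stated, and the sample size is correct for its stated purpose.
- *That the plan will treat non-significance as similarity.* It never says so.
- *That no between-group estimate is planned.* Section 8.2 plans one.
- *That every predictor named in 8.2 arises after treatment starts.* Section 6.1.2 defines time consumption to include travel, distance and waiting. The problem is that such variables may lie between setting and satisfaction. The list is also only of examples.

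What the reply does not remove is that the one quantity bearing on similarity is not named as the primary result and has no stated interval or baseline adjustment set. For a descriptive study, that difference with its interval is the natural main result.

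**Conclusion.** The point holds in this limited form and should be fixed before the data are analysed. The plan motivates the study by similarity but names group-wise intervals and difference tests, which cannot show it. With 100 complete cases per group, a true deficit of 0.3 SD would be missed in 44% of studies, and in about 33% of all studies the interval would still include a deficit of 0.4 SD.

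These figures assume equal groups, a common SD and no change in precision from adjustment. The true deficits and the 20% loss are assumptions, since the documents give neither. The gap is in specification and wording; the planned data remain usable.

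**What to change.** 1. **Section 8.1.** Make the primary result the difference in mean 12-week PSQ-18 score, practice minus hospital, with its 95% interval. Give it unadjusted, and adjusted for age, sex, socioeconomic status, and location and severity of the trauma (section 6.1.3). Comorbidity appears among the Summary determinants but has no data item in section 6, so add it only if it is recorded.
2. **Section 8.2.** Keep complications, pain, physical functioning, EQ-5D and time consumption for the determinants analysis, and out of the model for the setting comparison.
3. **Wording.** State in 8.1 that a non-significant difference will not be reported as similarity. In the Summary and section 1, limit the sentence on similar results to what the interval for the 12-week satisfaction difference excludes.
4. **Optional.** Only if a formal non-inferiority or equivalence claim is intended, fix and justify a PSQ-18 margin before analysis. The 0.4 SD in section 4.4 should not become the margin by default.

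The cost is a few sentences. Items 1 to 3 need no extra patients, visits or questionnaire items, as the listed covariates are already planned. The downside is that the substitution claim becomes more modest and may be inconclusive at 200 patients.
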